### 3. LIST OF ABBREVIATIONS AND DEFINITIONS OF TERMS

**Table 3: Abbreviations and Specialist Terms**

Abbreviation or specialist term	Explanation
ADL	Activities of Daily Living
ADR	Adverse drug reaction
AE	Adverse event
AESI	Adverse event of special interest
AF	Aggressive Fibromatosis
AKT	Protein Kinase B
ALT	Alanine Aminotransferase
AMH	Anti-Müllerian Hormone
ANC	Absolute Neutrophil Count
ARAs	Acid Reducing Agents
AST	Aspartate Aminotransferase
BEP	bleomycin, etoposide, plus cisplatin
Bcl-2	B-cell lymphoma 2
BID	Twice daily
C	Cycle
CA 125	Cancer Antigen 125
CFR	Code of Federal Regulations
CI	Confidence Interval
CIOMS	Council for International Organizations of Medical Sciences
CKD-EPI	Creatinine Kinase Disease Epidemiology Collaboration
C max	Maximum plasma concentration
C trough	Plasma trough concentration
CONSORT	Consolidated Standards of Reporting Trials
COVID-19	Coronavirus Disease 2019
CPK	Creatine phosphokinase
CR	Complete response
CRF	Case report form
CSR	Clinical Study Report
CT	Computed tomography
CTCAE	Common Terminology Criteria for Adverse Events
ctDNA	Circulating tumor DNA

Abbreviation or specialist term	Explanation
CXR	Chest x-ray
CYP2B6	Cytochrome P450 2B6
CYP2C8	Cytochrome P450 2C8
CYP2C9	Cytochrome P450 2C9
CYP3A4	Cytochrome P450 3A4
D	Day
DAPT	r N-[N-(3,5- difluorophenacetyl)-L-alanyl]-S-phenylglycine t-butyl ester
DDI	Drug-drug interaction
DNA	Deoxyribonucleic acid
DT	Desmoid tumor
DTP	Direct to Patient
ECG	Electrocardiogram
ECOG	Eastern Cooperative Oncology Group
eCRF	Electronic case report form
EDC	Electronic Data Capture
eGFR	Estimated Glomerular Filtration Rate
EOT	End of Treatment
Fas	Apoptosis antigen 1
FDA	Food and Drug Administration
FFPE	Formalin-Fixed Paraffin-Embedded
FIGO	International Federation of Gynecology and Obstetrics
FOSI	Functional Assessment of Cancer Therapy – Ovarian Symptom Index
FOXL2	Forkhead box protein L2
FOXO1	Forkhead box protein O1
FOXO3	Forkhead box protein O3
FSH	Follicle-stimulating hormone
FUP	Follow-up
GCP	Good Clinical Practice
GCT	Granulosa cell tumors
GOG	Gynecologic Oncology Group
GS	$\gamma$ -secretase
H2	Histamine 2
HBsAg	Hepatitis B surface antigen
HBV	Hepatitis B virus

Abbreviation or specialist term	Explanation
HCT	Hematocrit
HCV	Hepatitis C virus
Hes1	Hairy and Enhancer of Split 1
Hes4	Hairy and Enhancer of Split 4
HGB	Hemoglobin
HIPAA	Health Insurance Portability and Accountability Act
HRT	Hormonal Replacement Therapy
HT	Hormonal therapy
HIV	Human immunodeficiency virus
HPLC	High performance liquid chromatography
HR	Heart rate
IB	Investigator Brochure
ICF	Informed Consent Form
ICH	International Conference on Harmonization
IEC	Independent ethics committee
IgG	Immunoglobulin G
IHC	Immunohistochemistry
INR	International normalized ratio
IRB	Institutional Review Board
IRT	Interactive Response Technology
IUD	Intrauterine device
IUS	Intrauterine hormone releasing system
K-M	Kaplan-Meier
LD	Longest dimension
LDH	Lactate dehydrogenase
LH	Luteinizing Hormone
MIS	Müllerian Inhibiting Substance
MRI	Magnetic Resonance Imaging
MTD	Maximum tolerated dose
N	Sample size
NE	Not evaluable
NGS	Next Generation Sequencing
NICD	Notch Intracellular Domain
No.	Number

Abbreviation or specialist term	Explanation
NOBOX	Newborn ovary homeobox protein
ORR	Objective Response Rate
OS	Overall survival
OvGCT	Ovarian granulosa cell tumors
PCR	Polymerase chain reaction
PD	Progressive Disease
PFS	Progression free survival
PFS2	Progression free survival 2
PFS-6	Progression free survival at 6 months
P-gp	P-glycoprotein
pH	potential Hydrogen
PI3K	Phosphoinositide 3-kinases
PK	Pharmacokinetics
PPI	Proton pump inhibitor
POF	Primary ovarian failure
POI	Primary ovarian insufficiency
PR	Partial Response
PRO	Patient-reported outcomes
PTEN	Phosphatase And Tensin Homolog
QD	Once daily
QRS	QRS complex
QT	Uncorrected QT interval
QTc	Corrected QT interval
QTcF	Corrected QT interval by Fredericia
RECIST	Response Evaluation Criteria in Solid Tumors
RNA	Ribonucleic acid
RP2D	Recommended phase 2 dose
RSI	Reference safety information
SAE	Serious adverse event
SAP	Statistical Analysis Plan
SAR	Serious adverse reaction
SCST	Sex cord-stromal tumor
SD	Stable disease
SGOT	Serum glutamic-oxaloacetic transaminase

Abbreviation or specialist term	Explanation
SGPT	Serum glutamic-pyruvic transaminase
SMAD	Mothers against decapentaplegic homolog
SoA	Schedule of Assessments
SUSAR	Suspected Unexpected Serious Adverse Reactions
TdP	Torsades de Pointes
TEAE	Treatment Emergent Adverse Event
TGF- $\beta$	Transforming growth factor- $\beta$
TKI	Tyrosine kinase inhibitors
TNF-R1	Tumor Necrosis Factor R1
TRAIL R1	Tumor Necrosis Factor – Related Apoptosis-Inducing Ligand R1
ULN	Upper Limit of Normal
US	United States
WNT4	Wingless/integrated Family Member 4
WOCBP	Woman of Childbearing Potential

## 4. INTRODUCTION

SpringWorks Therapeutics is developing nirogacestat which is a potent, small molecule, selective, reversible, non-competitive inhibitor of  $\gamma$ -secretase (GS) for the treatment of desmoid tumors (DT). The rationale for developing a GS inhibitor in cancer is supported by emerging evidence that Notch signaling, activated by GS cleavage, can drive the growth of a wide range of tumors.

### 4.1. STUDY RATIONALE

The purpose of this phase 2, single-arm study is to assess the anti-tumor activity of nirogacestat in adult participants with relapsed/refractory ovarian granulosa cell tumors (OvGCTs). In ongoing clinical trials for desmoid tumors, effects on ovarian function have been reported for female participants receiving nirogacestat. High levels of Follicle-stimulating hormone (FSH) not typical in pre-menopausal women have been detected in this study and are consistent with pituitary response to decreased sex steroid production.

These effects appear to be the result of NOTCH inhibition in human ovaries by nirogacestat. Further support for this suggested mechanism was seen in pre-clinical mouse models. These models show that the Notch signaling pathway, particularly the NOTCH 2 protein, is important in the differentiation and proliferation of ovarian granulosa cells ([Zhang et al. 2011](#); [Prasasya and Mayo 2018](#)). The results from the clinical trials for desmoid tumors, strongly support that nirogacestat is capable of inhibiting NOTCH function in the growth of desmoid tumors the mechanism of which should translate to the development and growth of OvGCTs.

Standard of care treatment for relapsed/refractory OvGCT is platinum-based chemotherapy consisting of bleomycin, etoposide, and cisplatin or carboplatin and paclitaxel. These chemotherapy regimens, however, are not associated with durable remissions and most patients eventually develop progressive disease (PD) necessitating treatment with experimental agents. In prior studies in progressive OvGCTs, experimental agents have shown promise with only modest performance. In the Gynecologic Oncology Group (GOG) study of bevacizumab monotherapy, the Objective Response Rate (ORR) was 16.7% with a median Progression Free Survival (PFS) of 9.3 months ([Brown et al. 2014](#)). Combination therapy of bevacizumab with paclitaxel showed an improved ORR of 44% compared to 25% for paclitaxel monotherapy but did not improve PFS ([Ray-Coquard et al. 2020](#)).

Our hypothesis is that treatment of relapsed/refractory OvGCT with nirogacestat 150 mg twice daily (BID) will provide at least ORR of 30% with a secondary objective of improved duration of PFS and Overall Survival (OS) compared to bevacizumab monotherapy. Refer to [Table 4](#) for study Objectives and Endpoints.

### 4.2. BACKGROUND

Granulosa cell tumors (GCT) of the ovary belong to the ovarian sex cord-stromal tumors (SCSTs), a group of benign and malignant neoplasms that develop from the sex cord (e.g., granulosa cell tumors, Sertoli cell tumors) or stromal cells (e.g., Leydig cell tumors, fibromas) or

both. Granulosa cell tumors are the most common type of malignant ovarian SCSTs comprising 90% of malignant SCSTs and 2 to 5 percent of all ovarian malignant neoplasms (Quirk and Natarajan 2005; Young 2005). Granulosa cell tumors of the ovary are divided into adult and juvenile types based on different clinical and histopathologic features (Schumer and Cannistra 2003). The juvenile type represents only 5% of cases and usually occurs in prepubertal girls and women younger than 30 years (Young 2005; Powell et al. 1993). The adult type most commonly presents during the perimenopausal or early postmenopausal period, with a median age of diagnosis between 50 and 54 years (Dridi et al. 2018; Kottarathil et al. 2013). There are no widely accepted clinically defined risk factors for this disease. Importantly, unlike epithelial ovarian cancer, there seems to be no known inherited predisposition for the development of these tumors, i.e. no association with germline mutations in BRCA1 and BRCA2 genes and no association with germline mutations in mismatch repair genes (Schumer and Cannistra 2003; Färkkilä et al. 2017).

Abdominal pain and abnormal uterine bleeding are the most common presenting symptoms (Koukourakis et al. 2008). Abdominal pain is related to the fact that GCTs can be hemorrhagic and large. Given its highly vascular nature, GCTs may occasionally present with hemorrhagic rupture of the tumor into the abdominal cavity and development of hemoperitoneum (Schumer and Cannistra 2003; Färkkilä et al. 2017; W.-L. Lee et al. 1999). Postmenopausal bleeding is due to prolonged exposure of the endometrium to tumor-derived estradiol, resulting in endometrial hyperplasia or endometrial adenocarcinoma. In premenopausal women, menstrual irregularity, menorrhagia, or even secondary amenorrhea may be the initial manifestation, while rarely, infertility (possibly due to increased inhibin secretion) may be the initial manifestation (Dridi et al. 2018; Segal, DePetrillo, and Thomas 1995). In premenarchal girls, isosexual precocious pseudo-puberty may be the initial presentation (Levin et al. 2018).

Microscopically, GCTs consist of small, round or oval granulosa cells with characteristic “coffee-bean” nuclei (Young 2005; King et al. 1996). Call-Exner bodies are characteristic of granulosa cell tumors and appear in 30% to 60% of cases; these constitute small cystic areas of fluid and cellular debris surrounded by well-differentiated granulosa cells (Young 2005; Ranganath R. et al. 2008). Call-Exner bodies and coffee-bean grooved nuclei are infrequent in the juvenile type of granulosa cell tumors (Powell et al. 1993; Ranganath R. et al. 2008).

Granulosa cell tumors are hormonally active and therefore several tumor markers have been used for postoperative surveillance and evaluation of response to therapy. Although estradiol may be helpful in monitoring the status of some patients, it is not a reliable marker because of a lack of consistent correlation between estradiol levels and tumor burden as well as disease progression; of note, absence of estradiol secretion is observed in approximately 30% of patients (Schumer and Cannistra 2003; Lappöhn et al. 1989). Inhibin is a more reliable marker of disease activity than estradiol and can serve as a useful marker of GCT activity in both pre- and postmenopausal women (Lappöhn et al. 1989). The alpha subunit of inhibin may associate with one of two distinct beta subunits, leading to the formation of either inhibin A or inhibin B. Although both inhibins may serve as tumor markers and should both be evaluated, inhibin B is more frequently elevated in patients with this disease (Robertson et al. 1999). Anti-müllerian

hormone (AMH), also referred to as Müllerian inhibitory substance (MIS) is another tumor marker for GCTs in postmenopausal and post-oophorectomy women (Färkkilä et al. 2017; Long et al. 2000). AMH is produced by the granulosa cells in the developing follicles of the ovary and AMH levels are elevated in a cyclical fashion throughout reproductive life but become undetectable in the postmenopausal period (Long et al. 2000).

Molecularly, the pathognomonic somatic missense point mutation 402C->G (C134W) in FOXL2 has been identified in 97% of adult subtype GCTs but only in 1 of 10 juvenile granulosa cell tumors (Shah et al. 2009). FOXL2 encodes a transcription factor that is expressed as a nuclear protein and is critically important in the development of granulosa cells. The FOXL2 C134W mutation leads to increased proliferation and survival of granulosa cells, and promotes hormonal changes (Färkkilä et al. 2017; Jamieson and Fuller 2012). The exact mechanism of how the FOXL2 mutation causes tumor formation is not completely understood. At the molecular level, the C134W mutation is not linked to alterations in the protein structure, but instead causes a change in the posttranslational modification (ubiquitination) leading to impaired interactions of FOXL2 with other transcription factors leading to subtle changes in the transcription of target genes (Färkkilä et al. 2017; Jamieson and Fuller 2012).

The staging system for GCTs is generally the same International Federation of Gynecology and Obstetrics (FIGO) staging used for epithelial ovarian cancer (Prat 2015). Surgery is the cornerstone of initial management for patients with GCTs (Schumer and Cannistra 2003; Powell et al. 1993; Segal, DePetrillo, and Thomas 1995; Peiretti et al. 2020). Surgery is necessary to establish a definitive diagnosis, perform staging, and remove as much tumor as possible with surgical principles being essentially identical to those used in the management of epithelial ovarian cancer (Peiretti et al. 2020; Abu-Rustum et al. 2006; Kuru et al. 2017; Ottolina et al. 2015; Stine, Pierce, and Soper 2014). Surgery typically includes total hysterectomy and bilateral salpingo-oophorectomy; conservation of a contralateral ovary and/or the uterus (if it has no evidence of disease) is reasonable in younger women with stage IA disease who wish to preserve fertility. This fertility-sparing approach recognizes the fact that GCTs are unilateral in more than 90% of cases. Surgery alone is acceptable treatment for patients with stage IA (Iyibozkurt et al. 2010). For those with stage IC and above, adjuvant chemotherapy is recommended, either the bleomycin, etoposide, plus cisplatin (BEP) regimen or the paclitaxel plus carboplatin regimen (Schumer and Cannistra 2003; Färkkilä et al. 2017; Iyibozkurt et al. 2010). For patients with stage IIA to IV disease or those with chemo-naïve disease, an ongoing randomized clinical trial (GOG264) is investigating carboplatin/paclitaxel vs BEP as the optimal first-line regimen in this disease (NCT01042522).

Treatment of recurrence involves surgery if the recurrent disease is resectable followed by postoperative platinum-based chemotherapy; postoperative radiation or observation can also be considered (Wolf et al. 1999; Hauspy et al. 2011). If disease is unresectable or the patients are not surgical candidates, platinum-based chemotherapy, endocrine therapy, and antiangiogenic therapy have shown activity in that setting. Chemotherapeutic regimens for recurrent disease may include BEP or carboplatin/paclitaxel depending on which regimen was used previously. However, no chemotherapy regimen is associated with durable remissions and the majority of

patients eventually experience progressive disease. Hormonal therapies such as luteinizing hormone-releasing hormone agonists (e.g., leuprolide), aromatase inhibitors, tamoxifen alone, progesterone alone, or a combination of tamoxifen and progesterone have been associated with long-term responses in some patients; however, most patients do not respond or exhibit brief responses (Hardy et al. 2005). Finally, antiangiogenic therapy with bevacizumab has shown promise; in a GOG phase II trial of bevacizumab in patients with metastatic SCSTs (89% were granulosa cell tumors) the objective response rate was 16.7% with stable disease in 77.8 percent of patients and a median progression-free survival of 9.3 months (Brown et al. 2014). Overall, there are currently no effective salvage therapies for patients with recurrent disease and, unlike epithelial ovarian cancer, there are currently no Food and Drug Administration (FDA) approved therapies, specific for granulosa cell tumors. Therefore, there is an urgent unmet need for novel therapies for granulosa cell tumors, especially targeted therapies based on a deeper understanding of the pathogenesis of these tumors and the role of the pathognomonic FOXL2 mutation.

#### **4.3. BENEFIT/RISK ASSESSMENT**

To date, the safety profile of single agent nirogacestat in participants with advanced cancer has been characterized by manageable and reversible toxicities. Currently, important identified risks related to nirogacestat include diarrhea, dermatologic reactions (maculopapular rash, hidradenitis, and folliculitis), ovarian dysfunction, electrolyte abnormalities (hypophosphatemia and hypokalaemia), and elevated liver transaminases. Important potential risks include embryofetal toxicity, effects on male fertility and in pediatric patients, epiphyseal disorder. The results of the nonclinical toxicology and safety pharmacology studies, together with the clinical experience in patients with advanced cancers, support the hypothesis that nirogacestat may represent an important therapeutic approach in patients with GCTs. Thus, the projected benefit/risk balance is considered favorable for further development in this patient population.

More detailed information about the known and expected benefits and risks and reasonably expected AEs of nirogacestat may be found in the Nirogacestat Investigator's Brochure.

## 5. OBJECTIVES AND ENDPOINTS

**Table 4: Objectives and Endpoints**

Objectives	Endpoints
Primary Objective	Primary Endpoint
To determine the anti-tumor activity of nirogacestat in adult participants with relapsed/refractory OvGCT	Objective response rate (ORR) defined as the proportion of participants with Complete Response (CR) + Partial Response (PR) using RECIST v1.1 criteria
Secondary Objectives	Secondary Endpoints
To determine if nirogacestat delays progression or death in OvGCT	Estimate of proportion of participants who have not progressed or died at 6 months of follow-up: PFS-6. Progression is defined by RECIST v1.1
To describe overall survival in participants treated with nirogacestat	Estimate of 2-year overall survival, defined as the proportion of participants who have not died after 2 years of follow-up after their first dose of nirogacestat
To determine the effect of nirogacestat on ovarian cancer symptoms measured by Functional Assessment of Cancer Therapy – Ovarian Symptom Index (FOSI)	Change from baseline in FOSI
To determine the duration of response	Duration of response (DoR), defined as the time from first assessment of response (CR + PR using RECIST v1.1) to first disease progression defined by RECIST v1.1 or death, whichever comes first
To determine the pharmacokinetics (PK) of nirogacestat	Serum concentrations of nirogacestat will be measured to evaluate system exposures ( $C_{\max}$ , $C_{\text{trough}}$ and other PK parameters as data allow)
Safety Objectives	Safety Endpoints
To characterize the safety and tolerability of nirogacestat at a dose of 150 mg BID in adult participants with relapsed/refractory OvGCT	Key safety endpoints will include incidence of treatment emergent Adverse Events (TEAEs), changes in clinical laboratory parameters, vital signs, physician examination findings, and electrocardiograms (ECGs). Tolerability will be assessed according to toxicities graded by National Cancer Institute Common Terminology Criteria for Adverse Events (CTCAE) v5.0
Exploratory Objectives	Exploratory Endpoints
To detect FOXL2 C134W mutation as well as other genomic alterations and correlate these with response	Evaluate NGS status in baseline tumor tissue
To detect NICD and candidate biomarkers of response, and to correlate nirogacestat exposure with response	Evaluate change from Baseline: 
 
Inhibin A&B, Follicle-stimulating hormone (FSH), estradiol, CA-125 and Müllerian Inhibiting Substance (MIS) / AMH
 
Circulating tumor DNA (ctDNA)
 
 Baseline NICD expression in tumor tissue

To describe progression free survival on continued nirogacestat treatment post first disease progression	Progression free survival on prolonged nirogacestat treatment, defined as time from first disease progression per RECIST v1.1 to second disease progression on continued nirogacestat treatment confirmed by investigator discretion or death, whichever comes first
To describe progression free survival on subsequent line of anticancer treatment	Progression free survival 2 (PFS2), defined as time from first dose of nirogacestat to second disease progression on subsequent line of anticancer treatment (after nirogacestat) confirmed by investigator discretion at long term safety follow-up visit or death, whichever comes first

## 6. STUDY DESIGN

### 6.1. OVERALL DESIGN

This is a multi-center, single-arm, Phase 2 open label treatment study to determine the efficacy, safety, tolerability, and pharmacokinetics of nirogacestat in adult participants with relapsed/refractory OvGCT. Approximately 43 eligible participants will be enrolled. Participants must have received at least one prior course of systemic therapy for OvGCT and have measurable disease per RECIST v1.1 to meet eligibility criteria.

Participants will be screened up to 28 days prior to the first dose of study treatment (nirogacestat) and full eligibility will be based on inclusion and exclusion criteria ([Sections 7.1](#) and [7.2](#)). At Cycle 1 Day 1 (C1D1), eligible participants will enroll in the study using the Interactive Response Technology (IRT) system and will orally administer their first dose of study treatment (150 mg; nirogacestat) followed by a 1-hour observation period. Following C1D1, participants will orally administer 150 mg of study treatment twice daily (BID), continuously in 28-day cycles. Participants will return to the clinic for study visits monthly for the first year (C1-C13) and then every 3 months thereafter (C16 and On).

Participants will remain on study treatment until death, disease progression (unless the participants meet criteria for continued treatment as defined in [Section 9](#)) discontinuation of study treatment for any reason, the study is stopped by the Sponsor for any reason, or participant qualifies for Sponsor's Compassionate Use program (see [Section 9](#) for full discontinuation criteria).

Participants who discontinue study treatment early for any reason should return to the clinic for an End of Treatment (EOT) visit within 7 days after the Investigator determines study treatment will no longer be used and then again for a safety Follow-up (FUP) visit 30 days (+7 days) after the last doses of study treatment.

The estimated study duration is 3 years, and all participants will be followed for at least 2 years (unless the study is prematurely stopped due to futility).

This study will use a Bayesian predictive probability approach with early stopping guidelines based on objective tumor response rate (CR+PR) intended to limit the accrual of participants to ineffective treatments. There will be no pause in accrual for interim assessments.

After accrual of full sample size, estimated ORR will be calculated after the last participant completes 6 cycles of therapy and has re-imaging at C7D1.

Refer to the Schedule of Assessments (SoA) ([Section 1.3](#)) for details on assessments and timing of study visits.

Refer to [Section 1.2](#) for the study schema.

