## **8.4. DOSE MODIFICATION**

Every effort will be made to administer study treatment (nirogacestat) at 150 mg BID. However, dosing will be interrupted and/or dose reduced for the AEs described in [Table 7](#). Study treatment may also be modified to manage other AEs in collaboration with the Medical Monitor.

If an event listed in [Table 7](#) has an alternative etiology and is not considered study treatment related, dose modifications may not be required; consult with the Medical Monitor.

If a participant experiences an AE as described in [Table 7](#), hold study treatment until the AE is resolved to  $\leq$  Grade 1 or baseline.

- If the AE is resolved within 14 days, then study treatment should be restarted at the reduced dose as described in [Table 7](#).
- If the AE does not resolve to  $\leq$  Grade 1 or baseline after holding study treatment for 22 days, study treatment may be resumed only after discussion with the Medical Monitor.

Should the same  $\geq$  Grade 3 AE recur at the reduced dose, and the AE is considered related to the study treatment, study treatment may be permanently discontinued following discussion with the Medical Monitor.

An unscheduled visit may be performed at any time during the study. Assessments to be performed at the unscheduled visit will be determined by the Investigator.

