## 11.1. EFFICACY ASSESSMENTS

### 11.1.1. Tumor Imaging

Tumor response will be assessed by CT or MRI (contrast required unless contraindicated). The same imaging modality and radiographic procedure used to assess disease sites at Screening is required to be used throughout the study (i.e., the same contrast protocol for scans). Tumor response and progression of cancer under study in real time will be evaluated locally at each study site according to RECIST v1.1 ([Eisenhauer 2009](#)). See [Appendix 3](#) RECIST Criteria response definitions. All RECIST measurements will be done by the site's local radiologist.

Chest imaging using CXR or CT (contrast not required) will also be required as described in the SoA and should be obtained per institutional standards.

Standard of care scan(s) acquired prior to the participant signing ICF may be used as the participant's screening visit scans if they were obtained within 28 days of the first dose of study treatment.

On treatment scans may be acquired (-) 7 days prior to the study visit or within the study visit window as described in the SoA ([Section 1.3](#)).

Imaging must be done prior to tumor biopsy if assessments occur on the same day.

Whenever disease progression is suspected (e.g., symptomatic deterioration) throughout the study, unscheduled scans may be acquired.

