## Confirmation

- **Confirmation of response:**
  - The main goal of confirmation of objective response is to avoid overestimating the response rate observed. In cases where confirmation of response is not feasible, it should be made clear when reporting the outcome of such studies that the responses are not confirmed.
  - To be assigned a status of PR or CR, changes in tumor measurements must be confirmed by repeat assessments that will be performed no less than 4 weeks after the criteria for response are first met.
- **Confirmation of SD:** in the case of SD, follow-up measurements must have met the SD criteria at least once after study entry (signing of Informed Consent Form [ICF]) at a minimum interval of 8 weeks.

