1.3. Study Design

This is a multi-center, single-arm, Phase 2 open label treatment study to determine the efficacy, safety, tolerability, and pharmacokinetics of nirogacestat in adult participants with recurrent OvGCT. Participants must have received at least one prior course of systemic therapy for OvGCT and have measurable disease by RECIST v1.1 to meet the eligibility criteria.

The Schedule of Assessments (SoA) is in protocol Section 1.3, Table 2. Participants will be screened up to 28 days prior to the first dose of study treatment (nirogacestat) and full eligibility will be based on the inclusion and exclusion criteria (Protocol Section 7.1 and 7.2).

Participants will administer 150 mg (3 × 50 mg tablets) of study treatment BID, continuously in 28-day cycles. Participants will remain on study treatment until death, disease progression (unless the participants meet criteria for continued treatment), discontinuation of study treatment for any reason, the study is stopped by the Sponsor for any reason, or participant qualifies for Sponsor's Compassionate Use Program.

All scans will be performed and read locally by the site's radiologist for Tumor assessment as per RECIST v1.1. Same modality used at Screening must be used at each subsequent imaging visits. Baseline scan is defined as scans performed prior to first dose of study treatment. On treatment scans are performed every 8 weeks (C3D1, C5D1, C7D1) for the first 6 months and then every 12 weeks (C10D1, C13D1, etc.) thereafter. Scans may be performed (-) 7 days prior to the visit.

The final 2-year survival check-in will occur approximately 2 years after the first dose of study treatment. If participant discontinues from study treatment prior to the 2-year check-in, quarterly telephone or email contact following EOT is required until the 2-year survival data point has

been collected. In addition, collection of subsequent anticancer therapy after nirogacestat and overall response to this therapy will be recorded. Only information about the subsequent therapy used directly after nirogacestat is required along with the final survival outcome at the 2-year check point.

Participants who discontinue study treatment early for any reason should return to the clinic for an End of Treatment (EOT) visit within 7 days after the Investigator determines study treatment will no longer be used and then again for a safety Follow-up (FUP) visit 30 days (+7 days) after the last dose of study treatment.

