3. ENDPOINTS

3.1. Primary Efficacy Endpoint

The primary efficacy endpoint is objective response rate, defined as the proportion of participants with CR + PR using RECIST v1.1. See Section 8.1 for the details of RECIST Criteria v1.1.

Study participants who have no post-baseline tumor assessment and those whose best overall response is not evaluable or less than CR or PR will be analyzed as a non-responder.

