5.3. Primary Efficacy Endpoint

All efficacy endpoints will be analyzed using the Full Analysis Set. The primary efficacy endpoint is objective response rate, defined as the proportion of participants with CR + PR.

Tumor response and progression of cancer under study in real time will be evaluated locally at each study site according to RECIST v1.1.

To be assigned a status of PR or CR, changes in tumor measurements must be confirmed by repeat assessments that will be performed no less than 4 weeks after the criteria for response are first met. In order for a valid value of Stable Disease (SD) to be assigned, there must be evidence of stable disease for at least 7 weeks (the 8-week scan interval inclusive of a 1-week window per the SoA) from start of treatment. If the minimum time for SD has not been met on the first assessment, the assignment of BOR will depend on subsequent response assessments.

Participants who do not have follow up data after a first assessment of SD prior to the minimum time requirement will be considered as not evaluable (NE).

The best overall response is determined by the following hierarchy: CR > PR > SD > PD > NE. Participants with a best overall response as confirmed CR or PR during the study will be

responders. Participants who had no post-baseline tumor assessment and those whose best overall response is no evaluable or less than CR or PR will be analyzed as non-responders.

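### The full-sample ORR may be run at the last C7D1 scan, before responses first seen there can be confirmed on schedule; run then, it is biased modestly downward by enrolment date

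*Protocol*

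**What the plan says.** Protocol 6.1 gives the only timing in either document for the full-sample primary estimate: "estimated ORR will be calculated after the last participant completes 6 cycles of therapy and has re-imaging at C7D1".

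The response definition requires confirmation. Under Protocol Appendix 3 (Confirmation), the tumour changes behind a PR or CR "must be confirmed by repeat assessments that will be performed no less than 4 weeks after the criteria for response are first met". SAP 5.3 repeats the rule and adds: "Participants with a best overall response as confirmed CR or PR during the study will be" responders. SAP 3.1 states the converse: "those whose best overall response is not evaluable or less than CR or PR will be analyzed as a non-responder". Appendix 3 also has a reporting rule: "In cases where confirmation of response is not feasible, it should be made clear when reporting the outcome of such studies" that the responses are unconfirmed.

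SAP 1.3 places on-treatment scans "every 8 weeks (C3D1, C5D1, C7D1) for the first 6 months and then every 12 weeks (C10D1, C13D1, etc.) thereafter". The Schedule of Assessments (Protocol 1.3) puts C7D1 at Day 169 and C10D1 at Day 253.

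Off-schedule imaging is possible but not required for confirmation:

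- Protocol 8.4: "An unscheduled visit may be performed at any time during the study", with the assessments left to the investigator.
- Protocol 11.1.1: "unscheduled scans may be acquired" when progression is suspected.
- Schedule of Assessments, footnote 17c: an end-of-treatment scan is needed only if none was done in the previous 6 weeks.

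SAP 5.6.1 mentions a data cut-off conditionally, in the exposure rules. The SAP defines none for the ORR, and SAP 5.3.2 plans no ORR sensitivity analysis.

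**The concern.** The permitted trigger and the confirmation rule do not fit together. At the moment the last participant has the C7D1 scan, a response first seen on that scan cannot yet meet the 4-week minimum. On the planned schedule it cannot be confirmed for another 84 days. The same holds for everyone dosed less than 84 days before the last participant. For these people, whether a C7D1 response counts depends on when they enrolled and not on the drug.

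The only possible error is to count a responder as a non-responder, so the direction of the bias in the primary estimate is known in advance. Two statements in the documents make it relevant here. Protocol 6.2 says that responses to nirogacestat may be delayed. SAP 5.8 reports rapid accrual (53 enrolled before the one-year point), and faster accrual puts a larger share of participants inside the affected window.

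**Working it through.** **1. Visit days.** Visit day = 1 + 28 × (cycle − 1).

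- C7D1: 1 + 28 × 6 = 169. C10D1: 1 + 28 × 9 = 253. Both match the Schedule of Assessments.
- C3D1 to C5D1 and C5D1 to C7D1: 56 days each. C7D1 to C10D1: 253 − 169 = 84 days (75 to 93 if the −7/+2 day scan windows are used in full).

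A response first seen at C3D1 or C5D1 can therefore be confirmed on schedule by C7D1. One first seen at C7D1 cannot.

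**2. Participants affected.** The documents give no accrual dates, so uniform accrual over A days is assumed. The expected number dosed less than 84 days before the last participant, counting that participant, is 1 + N × 84/A.

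**3. Responders lost.** Lost = 0.30 × s × (1 + N × 84/A). Here 0.30 is the ORR the study aims for, and s is the assumed share of responders whose response is first seen at C7D1. All such responses are taken as confirmable, and the cut is made exactly at the trigger with no off-schedule scan.

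| N, accrual | Affected | s = 0.10 | s = 0.20 | s = 0.33 |
|---|---|---|---|---|
| 43, 12 months (365 days) | 1 + 9.9 = 10.9 | 0.33 | 0.65 | 1.08 |
| 43, 9 months (273 days) | 1 + 13.2 = 14.2 | 0.43 | 0.85 | 1.41 |
| 53, 12 months | 1 + 12.2 = 13.2 | 0.40 | 0.79 | 1.31 |
| 53, 9 months | 1 + 16.3 = 17.3 | 0.52 | 1.04 | 1.71 |

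A simulation with 40,000 replicates per cell gives the same values to within 0.02 responders. Divided by N, its losses are 0.74 to 3.29 ORR points. Among affected participants the expected counted rate is 0.30 × (1 − s): 27%, 24% or 20% for the three values of s, against 30% for earlier enrollees.

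**4. Variations (simulated).**

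| Scenario | Responders lost | ORR points |
|---|---|---|
| Cut at the trigger | 0.33–1.71 | 0.74–3.29 |
| Half confirmed off schedule | 0.16–0.86 | 0.38–1.65 |
| Cut 28 days after the trigger | 0.23–1.17 | 0.52–2.23 |
| Cut 56 days after the trigger | 0.13–0.64 | 0.29–1.25 |
| Cut at the last C10D1 scan | 0 for responses first seen by C7D1 | 0 |

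Full use of the scan windows widens the first row to 0.29–1.88 responders.

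**5. Scale.** The Clopper-Pearson interval for 13/43 is 17.2 to 46.1%, which reproduces Protocol Table 12. Its width is 46.1 − 17.2 = 28.9 points.

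**The case against.** The strongest reply is that the trigger is only a minimum. Protocol 6.1 says *after* the last C7D1 scan. SAP 5.3 counts confirmed responses over the whole study, and participants are followed for at least 2 years. The SAP's other outputs (2-year survival, PFS at 18 months and 2 years, an exposure category of 26 or more cycles) need mature data. An ORR run alongside them would not have this problem. That is correct as far as it goes. However, the 2-year text governs study duration and survival and does not set the ORR timing. Protocol 6.1 allows an earlier ORR, and no text requires a later one.

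Off-schedule scans could rescue some responses, but none is required. At the earliest cut, anyone dosed less than 28 days before the last participant could not meet the 4-week minimum even with an extra scan. That is about 4 people (1 + 43 × 28/365) to 6 people (1 + 53 × 28/273).

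Appendix 3 already asks for unconfirmed responses to be labelled where confirmation is not feasible. This helps the reader, but SAP 5.3 still counts them as non-responses.

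A C10D1 cut-off also leaves a similar gap for responses first seen at C10D1, since C13D1 (Day 337) is again 84 days later. By the formula above, each 10% of responders first seen there costs about 0.3 to 0.5 responders. This stands, and it is why the cut-off alone is not enough.

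Finally, the effect is small and conservative, and there is no formal hypothesis test. This also stands.

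**Conclusion.** The concern holds as a minor point. At the earliest time Protocol 6.1 permits, the full-sample ORR is biased downward, and only through participants enrolled in about the last 84 days of accrual. The gap, the confirmation rule and the direction come straight from the documents.

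The size, 0.3 to 1.7 responders or 0.7 to 3.3 ORR points, rests on assumptions the documents do not supply: a true ORR of 30%, uniform accrual over 9 to 12 months, 10 to 33% of responders first responding at C7D1, all of them confirmable, and no off-schedule confirmation. It omits responses first seen at C10D1 or later. The shift is small against an interval about 29 points wide.

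No decision rule is claimed to change. The criterion for calling the treatment promising is framed at the end of the study for 43 participants, and SAP 5.3.1 plans only the ORR and its interval. If the sponsor already intends a later cut, the loss shrinks or disappears, but that intention is not written down.

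**What to change.** In Protocol 6.1 and SAP 5.3.1:

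1. Set the primary ORR data cut-off at the point when every participant has had the C10D1 scan or has discontinued.
2. Count every response confirmed by that cut-off, whenever it was first seen, with no restriction to responses first seen by C7D1.
3. Report responses still awaiting confirmation separately, labelled as unconfirmed.
4. Update the ORR with all confirmed responses at the end of the study.

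Steps 3 and 4 cover late enrollees whose response is first seen at C10D1 or later.

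The cost is a readout up to about 12 weeks later, in a study that already follows participants for at least 2 years. No extra scans are needed, because C10D1 is already scheduled.
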